#### 2.1.5 Assess Impact of EQUIPPED on the Social Cognitive Factors Impact Individual Behavior Change

We will ask physicians at participating EDs to complete a brief survey at baseline, 6, and 12 months to assess key components of the SCT that we expect to be impacted by the intervention. This will allow us to determine if these components change and whether they are associated with the impact of the intervention on decisions made by individual providers. Measured components will include: 1) behavioral capability (knowledge of Beers List Medications); 2) expectations about the importance of addressing PIMs as defined by the Beers List; 3) self-control (believe that alternative medications are available); 4) reinforcement/information to monitor goals (use of EQUIPPED components at 6 and 12 months), and 5) self-efficacy for making changes. Similar to other studies on various provider behaviors and self-efficacy, for example, (e.g., provider panel management, provider implementation of motivational interviewing in primary care, and provider intentions to prescribe pre-exposure prophylaxis), survey questions will be developed specifically for this study and according to guidelines provided by Bandura (2006). The environment (i.e. system level factors) will be assessed through a formative evaluation of the implementation process supported by the SCT and particularly guided by the Organizational Theory of Implementation Effectiveness (OTIE). This survey will be fielded after it is approved by the IRB.

We will conduct statistical mediation analyses to test whether EQUIPPED changed the targeted intermediate variables of behavioral capability, expectations/expectancies, self-control, reinforcements, and self-efficacy (an ‘action test’) that are obtained through the survey described above; if change in these targeted intermediate variables was associated with a change in the % of prescriptions that represent PIMS (a ‘conceptual test’), and if EQUIPPED’s effects on this outcome variable were attributable to its effects on the intermediate variables (an ‘indirect effects’ or mediation test). The mediators will be tested simultaneously in order to determine the unique influence of each potential mediator. We plan for analyses will be conducted with

structural equation modeling using Mplus (version 6.11). However, other appropriate software may be utilized to analyze data from this study.

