be provided to the statistician based at the Birmingham site of the Birmingham/Atlanta GRECC each month for outcome assessment of PIM prescribing. In addition to feedback of individual prescribing patterns, providers also receive anonymous peer benchmarking comparing his/her individual performance to other ED providers at the same site (i.e., a scorecard of PIM prescriptions). This monthly feedback will come in the form of an emailed link to a clinical dashboard showing individual and site level prescribing data for each provider. No patient-identifiable health information will be included in the provider feedback form; however, site champions will have access to individual records if a provider would like to review specific cases to determine the appropriateness of a given prescription.

1.4.2 EQUIPPED with active provider feedback includes the same 3 components as those included previously with the addition of 1:1 in-person provider feedback using academic detailing.

- 1) The initial individual feedback session will be provided in-person to all staff providers (physician, APRN, PA). Clinical pharmacists or an ED provider may partner with the site champion to provide 1:1 feedback depending upon team composition at each site. In-person 1:1 provider feedback typically requires about 15 minutes and involves the following: a) an introduction of the provider's individual report structure and their baseline data as well as the current month's prescribing pattern; b) review the specific drug classes of PIMs that were prescribed during the reporting period; c) comparison of individual prescribing data to the cohort of peer providers within local ED; d) review of the top 5 PIM classes to avoid for the local ED; e) discussion of evidence-based alternative treatments appropriate for older adults; f) a brief demonstration of the EQUIPPED order set appropriate to that provider's needs based on prescribing of PIMs; and g) allowing time for provider question and discussion.
- 2) The onsite EQUIPPED champion will be an ongoing local expertise to provide consultation on clinical questions resulting from the 1:1 sessions such as consideration of appropriate medication alternatives.

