**Research Methods**

**2.0 Design**

In a parallel cluster randomized trial, we will randomize 8 VA facilities to implement the EQUIPPED QI intervention with either passive provider feedback (4 sites) or active provider feedback (4 sites). Specifically, it is anticipated that all sites will implement EQUIPPED components including: didactic education concerning the Beers Criteria; decision support by order sets; and monthly provider prescribing feedback. However, *passive* provider feedback sites will implement monthly provider feedback via an electronic dashboard with audit, feedback and peer benchmarking, while *active* provider feedback sites will implement one-to-one (1:1) in-person academic detailing from a professional colleague that includes in-person audit, feedback, and peer benchmarking and provide on-site expertise. To compare the effectiveness of EQUIPPED with in-person academic detailing including proactive feedback (*active feedback*) versus EQUIPPED with passive electronic audit and feedback (*passive feedback*) intervention, we will evaluate the monthly proportion of PIM prescribing as % of individual prescriptions (primary outcome) in each arm. It is hypothesized that the decline in PIM rates will be greater in the presence of EQUIPPED with active feedback compared to EQUIPPED with passive feedback.

After the initial recruitment and randomization, one of the eight sites had to pause order set development due to COVID-19 and an off-site detail of one of the core implementation team members. After several months of stalled progress with EQUIPPED implementation, the site decided to pause EQUIPPED implementation until at least spring 2021. We have recruited an additional site to fill the open study spot. We will continue to collect prescribing data from both sites and collect implementation evaluation data from the newly recruited facility based on the timeline for the award. If the initial facility determines they can move forward in 2021, we propose collecting implementation evaluation data as originally planned (would increase number of sites to n=9). The data analysis plan for this change is reflected below in section 2. 1. 3.

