In a parallel cluster randomized trial, we will randomize 8 VA facilities to implement EQUIPPED with either passive provider feedback or active provider feedback. Specifically, all sites will implement EQUIPPED components including: didactic education concerning the Beers Criteria; decision support by order sets; and monthly provider prescribing feedback. However, passive provider feedback sites will implement monthly electronic provider feedback via individual prescribing reports using a novel clinical dashboard with audit, feedback and peer benchmarking, while active provider feedback sites will implement one-to-one (1:1) in-person academic detailing that includes in-person audit, feedback, and peer benchmarking and engagement with an on-site champion. In order to inform the eventual dissemination strategy, we will also include formative evaluation and micro-costing of the two methods of implementing provider feedback as part of EQUIPPED. To assess the optimal implementation of EQUIPPED and overall program effectiveness, our specific aims are:

Specific Aim 1 (Primary Aim): To compare the effectiveness of EQUIPPED with in-person academic detailing including proactive feedback (*active feedback*) vs EQUIPPED with passive electronic audit and feedback (*passive feedback*) intervention by comparing the monthly proportion of PIM prescribing as % of individual prescriptions (primary outcome) in each arm. It is hypothesized that the decline in PIM rates will be greater in the presence of EQUIPPED with active feedback compared to EQUIPPED with passive feedback.

Specific Aim 2: Using a formative evaluation approach, we will evaluate the effectiveness of EQUIPPED implementation with passive feedback compared to EQUIPPED implementation with active feedback using including semi-structured qualitative telephone interviews and quantitative survey data.

Specific Aim 3: Using micro-costing methods, we will calculate the difference in the detailed cost of the passive vs. active feedback versions of EQUIPPED.

1. Rationale for the study sample size

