We will ask prescribers at participating EDs to complete a brief survey at baseline, 6, and 12 months to assess key components of the SCT that we expect to be impacted by the intervention. This will allow us to determine if these components change and whether they are associated with the impact of the intervention on decisions made by individual providers. Measured components will include:

1) behavioral capability (knowledge of Beers List Medications);

2) expectations about the importance of addressing PIMs as defined by the Beers List; 3) self-control (believe that alternative medications are available); 4) reinforcement/information to monitor goals (use of EQUIPPED components at 6 and 12 months), and 5) self-efficacy for making changes. Similar to other studies on various provider behaviors and self-efficacy, for example, (e.g., provider panel management,¹³ provider implementation of motivational interviewing in primary care,¹⁴ and provider intentions to prescribe preexposure prophylaxis¹⁵), survey questions will be developed specifically for this study and according to guidelines provided by Bandura (2006).¹⁶ The environment (i.e. system level factors) will be assessed through a formative evaluation of the implementation process supported by the SCT and particularly guided by the Organizational Theory of Implementation Effectiveness (OTIE).

Figure 2. Components of the Organizational Theory of Implementation Effectiveness (OTIE)

Steps in the Formative Evaluation Process at the Facility Level

- Collection of Baseline Characteristics that may Impact Implementation.** The eight sites will be asked to identify all individuals directly involved in the planning and execution of implementing EQUIPPED (e.g. clinical champions, ED Chiefs, pharmacists CACs). This is termed the core implementation team. Additionally, the eight sites will be asked to identify ED providers and staff that may encounter changed clinical decision-making as a result of implementation of the applications. These sites will be asked to complete a baseline site information document (1 site-level survey per site/medical center sent to the site

champion to be completed on behalf of the facility) that will collect information on core implementation team members and processes and size and composition of the medical centers and impacted clinical services.

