Aim 2: We will conduct statistical mediation analyses to test whether EQUIPPED changed the targeted intermediate variables of behavioral capability, expectations/expectancies, self-control, reinforcements, and self-efficacy (an 'action test'); if change in these targeted intermediate variables was associated with a change in the % of prescriptions that represent PIMS (a 'conceptual test'), and if EQUIPPED's effects on this outcome variable were attributable to its effects on the intermediate variables (an 'indirect effects' or mediation test).²⁹ The mediators will be tested simultaneously in order to determine the unique influence of each potential mediator. Analyses will be conducted with structural equation modeling using Mplus (version 6.11)³⁰

Aim 2: Linking Measures Within and Across Implementation Processes from Different Data Sources : We will combine quantitative measures of the degree of ORC, factors outlined in the OTIE that may influence implementation process, completeness of implementation progress, and sustainability to both implementation and intervention effectiveness outcomes. These data will be supplemented with qualitative data sources such as semi-structured individual interviews and supplemental process information. Inclusion of the qualitative component will enhance understanding of the local context. Quantitative and qualitative findings will produce mixed method findings to inform our understanding of the process of implementing EQUIPPED.

Aim 3: Not applicable for aim 3.

7. Methods for dealing with data transformations

Aim 1: Not applicable.

Aim 2: Generically not applicable. Individual scales will be calculated using published standards for each scale.

Aims 3: Not applicable.

8. Definitions of analytical sets

Aim 1: For the primary analysis related to the effectiveness of the EQUIPPED model to reduce the proportion of potentially inappropriate medications prescribed to older Veterans discharged from the ED, we will evaluate prescribing data according to intention to treat.

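### The mediation analysis takes EQUIPPED as its exposure, which both arms receive, and fixes no mediator wave, lag or outcome window

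*Protocol*

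**What the plan says.** **Exposure.** Protocol section 2.1.5 describes three linked tests. The action test is to "test whether EQUIPPED changed the targeted intermediate variables of behavioral capability, expectations/expectancies, self-control, reinforcements, and self-efficacy". The conceptual test relates change in those variables to change in the PIM percentage. The mediation test asks whether EQUIPPED's "effects on this outcome variable were attributable to its effects on the intermediate variables". SAP section 6, under Aim 2, repeats this and again sets out to "test whether EQUIPPED changed the targeted intermediate variables". Neither text names randomisation group as the exposure. SAP section 6 lists stratum and randomisation group for Aim 1 only.

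**Who receives EQUIPPED.** Protocol section 2.0 states that "it is anticipated that all sites will implement EQUIPPED components including: didactic education concerning the Beers Criteria; decision support by order sets", with monthly prescribing feedback as the third component. The SAP Introduction is firmer: "all sites will implement EQUIPPED components including" the same three. Under Protocol section 1.4.2 the active version "includes the same 3 components as those included previously with the addition of 1:1 in-person provider feedback using academic detailing"; champion consultation and on-screen alerts are listed there too.

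**Timing.** Protocol section 2.1.5: "We will ask physicians at participating EDs to complete a brief survey at baseline, 6, and 12 months". SAP section 2: "We will ask prescribers at participating EDs to complete a brief survey at baseline, 6, and 12 months". Reinforcement, defined as use of the EQUIPPED components, is listed at 6 and 12 months only. Prescribing is collected for 6 months before and 12 months after implementation (at least 12 in Protocol section 2.1.3). Neither document says which survey wave supplies the mediator or which outcome months it is related to.

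**Analysis set.** SAP section 8 limits the individual-level data to prescriptions by providers who volunteer for the surveys.

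**The concern.** A mediation analysis needs a contrast in exposure. Here the stated exposure is present everywhere after implementation and absent everywhere before it, so its effect on a mediator is simply the change over time. The study period includes COVID-19, which Protocol section 2.0 says halted progress at one site, so other causes of change are a realistic rival explanation. Self-selection into the survey adds to the difficulty.

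Separately, a mediator should precede the outcome it is said to explain. With no wave or lag fixed, an analyst could relate 12-month beliefs to prescribing that has already happened, and prescribing experience or feedback could have shaped the beliefs.

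What is at stake is the mechanism claim: the report could credit EQUIPPED, through self-efficacy or knowledge, with change that the design cannot attribute to it.

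**Working it through.** **1. The plan's own figures.** Protocol section 2.1.4 gives eight sites with at least 1,200 eligible prescriptions a year, that is 100 a month.
- Before: 8 × 100 × 6 = 4,800. After: 8 × 100 × 12 = 9,600. Both match.
- The stated near-100% power for 7.1% to 2.1% also reproduces (1.000, treating prescriptions as independent and assuming alpha 0.05). It concerns the primary outcome. No figure is stated for mediation.

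**2. Can an EQUIPPED effect be separated from time?** Take eight sites and survey waves at 0, 6 and 12 months, timed from each site's own start (an assumption). EQUIPPED is 0 at baseline and 1 afterwards.
- Site and wave terms: 8 + 2 = rank 10.
- Adding an EQUIPPED term: it equals the sum of the two post-baseline wave columns, so the rank stays 10. It is not separable from wave.
- Adding arm × post instead: rank 11. The active-versus-passive contrast is estimable.

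**3. How much of the outcome precedes each wave?** Assume the survey and outcome clocks both start at site implementation and the outcome covers months 1-12. The share before wave *w* is *w*/12, at 800 prescriptions a month.

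| Survey wave | Share before | Prescriptions before | Prescriptions after |
|---|---|---|---|
| Baseline | 0/12 = 0% | 0 | 9,600 |
| 6 months | 6/12 = 50% | 4,800 | 4,800 |
| 12 months | 12/12 = 100% | 9,600 | 0 |

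If the clocks differ by up to two months either way, the 6-month share runs from 4/12 = 33% to 8/12 = 67%, and the 12-month share is at least 10/12 = 83%.

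**4. Illustration of the exposure problem.** All values here are assumed: 120 providers (8 × 15); no effect of EQUIPPED or of arm; mediators rise and PIMs fall over time by 0.5 residual SD; a shared provider factor affects both changes; 2,000 runs. An indirect effect counts as found when both paths exceed 1.96 standard errors.

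| Loading on shared factor | Before-and-after EQUIPPED | Active vs passive |
|---|---|---|
| 0 | 5% | 0.3% |
| 0.3 | 15% | 1% |
| 0.5 | 60% | 3% |

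With the loading at 0.5 but no time trend, the before-and-after figure was 3.5%. The false finding therefore arises when a time trend and a shared cause act together. No within-site correlation was simulated, so the right-hand column does not show what only eight clusters would do.

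**The case against.** **EQUIPPED may be shorthand for arm.** This is the most natural defence, but it does not fit the text. Where the documents mean arm they say so: Protocol section 2.1.3 puts randomisation group in the Poisson model, and SAP section 6 lists it for Aim 1 immediately before the mediation paragraph, which omits it.

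**Start dates vary by site.** Staggered starts could in principle separate calendar time from exposure for the monthly outcome, but no calendar-time term is planned.

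**The plan does not choose the wrong wave.** This stands. A reader might infer that the mediators are measured after most of the outcome, or that the time order is reversed. The documents do not support that: there are three waves, the 6-month wave leaves half the post-implementation months still to come, and no pairing is stated. A reversed order is permitted, not prescribed.

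**Nurse practitioners and physician assistants are not shown to be excluded.** This also stands. A reader might infer exclusion from the protocol's reference to physicians, but the SAP surveys prescribers and SAP section 8 speaks of providers. It is a conflict to reconcile.

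**Changing the exposure does not by itself identify the indirect effect.** Correct. Randomising arm does not randomise the mediators, and a model of five simultaneous mediators would rest on eight clusters. The fix has to say so.

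**This is a supporting analysis.** True; the primary comparison already uses randomisation group.

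**Conclusion.** Wrong as written on the exposure, and open on timing. The action test and the indirect effect are defined on EQUIPPED, for which no arm is a comparator, so they are uncontrolled before-and-after quantities in a volunteer subset. This rests on the documents' own description of the arms; the rank result further assumes that surveys are timed from each site's start.

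It does not follow that no indirect effect can be estimated. The active-versus-passive version can be estimated from the planned data, on the assumption of no unmeasured mediator-outcome confounding and with few clusters.

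On timing, about 100% of a months 1-12 outcome precedes the 12-month survey and about 50% precedes the 6-month survey, on the common-clock assumption. The simulated percentages show direction under assumed values and do not predict this trial's error rate. The point is worth correcting because it governs the mechanism claim.

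**What to change.** In Protocol section 2.1.5 and SAP section 6:

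1. Name randomised arm (active versus passive) as the mediation exposure, with stratum as a covariate and site as the cluster. Label any before-and-after EQUIPPED mediation result descriptive.
2. Fix the time order in advance. One option is the 6-month mediator adjusted for its baseline value, related to the provider's PIM rate in months 7-12 adjusted for the baseline PIM rate. Use reinforcement at its 6-month value, since no baseline wave is planned for it. A lagged three-wave model within the planned structural equation framework would also serve if specified beforehand.
3. State that the indirect effect still assumes no unmeasured mediator-outcome confounding, and that it rests on eight clusters.
4. Include the non-randomised site added to the active group only in a sensitivity analysis.
5. Reconcile physicians (Protocol section 2.1.5) with prescribers (SAP section 2). Protocol section 1.4.2 gives the initial individual session to physicians, APRNs and PAs.

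The cost is wording; the surveys and provider-level prescribing data are already planned. The downside of the months 7-12 option is that about half the post-implementation data enters the mediation model: 4,800 of the planned minimum 9,600 prescriptions, before restriction to survey completers.

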## 2.2 Aim 2: Determination of Factors Affecting Organizational Adoption of EQUIPPED

We will conduct an in-depth, theory-based formative evaluation of sites, with the goals of understanding: 1) factors that may impact organizational readiness to implement EQUIPPED (i.e., organizational readiness for change (ORC)) and implementation of the EQUIPPED as outlined in the Organizational Theory of Implementation Effectiveness (OTIE); 2) changes in these factors over the course of one year; and 3) association between ORC and factors suggested by the OTIE to both successful implementation and sustainability over time. We will utilize a mixed-methods approach to measure ORC and change in related components over time. The ultimate goal is to inform the process of implementing EQUIPPED and be able to interpret potential results of the behavior change intervention regardless of primary trial outcome.

Further, we will inform the implementation of future provider behavior change programs. Table 1 below details factors that will be examined using the OTIE through the formative evaluation. Definitions are those developed by Bryan Weiner based on his adaptations of work by Klein and Sorra. The numbers in the table referring to data collection processes correspond to section 2.2.1 below. Other applicable theories, frameworks, or related concepts may be considered during data analysis.

Table 1: OTIE Factors Assessed through Formative EQUIPPED Evaluation		
Factor	Definition	Data Collection Process
Pre-and Early Implementation of EQUIPPED – Factors Expected to Impact the Readiness of Sites to Implement EQUIPPED		
Change Valence	Value that organizational members ascribe to a proposed change (i.e., its perceived attractiveness).	2
Task Demands	Knowledge about the tasks that need to be performed, the resources (human, financial and material) that are needed, and the time and effort that are needed to implement the intervention.	2
Resource Availability	Accessibility of financial, material, or human assets that can be used to support initial and ongoing innovation use.	1,2
Situational Factors	Contextual elements that affect the confidence and commitment of organizational members to implement the intervention.	2
Organizational Readiness for Change/To Implement EQUIPPED		
Organizational Readiness for Change (ORC)	Extent to which targeted organizational members are prepared to make the changes in organizational policies and practices that are necessary to put an innovation into practice and support its use. This is based on 2 factors: 1) commitment to change and 2) change efficacy.	2
Process of EQUIPPED Implementation		

Implementation Policies and Practices (IPPs)	Plans, practices, structures, and strategies that an organization employs to put the innovation into place to support innovation use	3,5
Implementation Climate	Shared perceptions of implementation policies and practices in terms of their meaning and significance for innovation use  .	3,5
Innovation-Values Fit	Extent to which implementers and users perceive that innovation use will foster the fulfillment of their values  . Values are concepts or beliefs that (a) pertain to desirable end-states or behaviors, (b) transcend specific situations, and (c) guide the selection and evaluation of behavior and events  .	3,5
Innovation-Task Fit	Extent to which the innovation is compatible with task demands, work processes, and organizational capabilities.	3,5
EQUIPPED Effectiveness and Sustainability		
Implementation Effectiveness	Consistency, quality, and appropriateness of innovation use within an organization  .	4,5
Innovation Effectiveness	Benefits an organization realizes from an innovation  (i.e., did EQUIPPED lead to a reduction in PIMs).	Trial outcome
Sustainability	Expected ability to continue to utilize EQUIPPED following the study.	6

